8.2 Quality of Life

Patient reported outcomes will be assessed at four time points:

- 1) Once at the pre-study visit.
- 2) At week 6 post-surgery
- 3) At months 3 and 6 in follow-up (post-op)

A Phase II Trial Evaluating Quality of Life After HIPEC in Patients with Stage IIIC and IV Ovarian, Fallopian Tube or Primary Peritoneal Carcinoma
Wake Forest Baptist Comprehensive Cancer Center (WFBCCC)
CCCWFU 83216

Patients' QOL, neurological symptoms and abdominal discomfort will be assessed with patient self-administered questionnaires.

QOL will be measured using the Functional Assessment of Cancer Therapy-Ovarian (FACT-O) questionnaire. The FACT-O is a multidimensional QOL questionnaire developed and validated for use by ovarian cancer patients; it includes 4 subscales: Physical Well-Being (7 items), Social Well-being (7 items), Functional Well-Being (7 items), Emotional Well-Being (6 items) and Additional Ovarian Cancer Concerns (12-items). These subscales can be analyzed separately or aggregated to produce a total score. The FACT-O has demonstrated reliability, validity, and responsiveness to change over time 31 as well as sensitivity to improvements in QOL experienced by patients responding to platinum/taxane therapy. The 4-item FACT/GOG-NTX4 (neurotoxicity) subscale will be used to assess patient reported symptoms of neurotoxicity. The FACT-GOG/Abdominal Discomfort (AD) measure will be used to assess abdominal discomfort. The FACT/GOG-AD is a four item measure (two included in the FACT-O) which measures abdominal symptoms, with average inter-item correlations of 0.64, an internal consistency of 0.875, and responsiveness to change over time computed on study data prior to the 4th cycle of chemotherapy by Huang, et al 2007.¹⁵

8.5 Methods for Evaluation of Measurable Disease

All measurements should be taken and recorded in metric notation using a ruler or calipers. All baseline evaluations should be performed within 90 days of registration prior to surgery.

The same method of assessment and the same technique should be used to characterize each identified and reported lesion at baseline and during follow-up. Imaging-based evaluation is preferred to evaluation by clinical examination when both methods have been used to assess the antitumor effect of a treatment.

Clinical lesions: Clinical lesions will only be considered measurable when they are superficial (e.g., palpable abdominal masses). In the case of palpable lesions, documentation by color photography, including a ruler to estimate the size of the lesion, is recommended.

Chest X-ray: Lesions on chest x-ray are acceptable as measurable lesions when they are clearly defined and surrounded by aerated lung. However, CT is preferable.

Conventional CT and/or MRI: These techniques should be performed with cuts of 5 mm or less in slice thickness contiguously. Spiral CT should be performed using a 2.5 mm contiguous reconstruction algorithm. This applies to tumors of the chest, abdomen, and pelvis.

Tumor markers: Tumor markers alone cannot be used to assess response. If markers are initially above the upper normal limit, they must normalize for a patient to be considered in complete clinical response.

Cytology & Histology: These techniques can be used to differentiate between partial responses (PR) and complete responses (CR) in rare cases (e.g., where known residual benign tumors can remain).

The cytological confirmation of the neoplastic origin of any effusion that appears or worsens during treatment when the measurable tumor has met criteria for response or stable disease is

A Phase II Trial Evaluating Quality of Life After HIPEC in Patients with Stage IIIC and IV Ovarian, Fallopian Tube or Primary Peritoneal Carcinoma
 Wake Forest Baptist Comprehensive Cancer Center (WFBCCC)
 CCCWFU 83216

mandatory to differentiate between response or stable disease (an effusion may be a side effect of the treatment) and progressive disease.

The best overall response is the best response recorded from the start of the treatment until disease progression/recurrence (taking as reference for progressive disease the smallest measurements recorded since the treatment started). The patient's best response assignment will depend on the achievement of both measurement and confirmation criteria.

Target Lesions	Non-Target Lesions	New Lesions	Overall Response	Best Response for this Category Also Requires:
CR	CR	No	CR	>4 wks. confirmation
CR	Non-CR/Non-PD	No	PR	>4 wks. confirmation
PR	Non-PD	No	PR	
SD	Non-PD	No	SD	Documented at least once >4 wks. from baseline
PD	Any	Yes or No	PD	no prior SD, PR or CR
Any	PD*	Yes or No	PD	
Any	Any	Yes	PD	

* In exceptional circumstances, unequivocal progression in non-target lesions may be accepted as disease progression.

Note: Patients with a global deterioration of health status requiring discontinuation of treatment without objective evidence of disease progression at that time should be reported as "*symptomatic deterioration*". Every effort should be made to document the objective progression even after discontinuation of treatment.

8.6 Methods for Evaluation of Survival

Disease-free Survival: Disease-free survival will be measured from the time of completion of treatment until the first date that recurrent or progressive disease is objectively documented (taking as reference for progressive disease the smallest measurements recorded since the treatment started).

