2.2 Secondary Objective(s)

- 2.2.1 To describe the QOL in patients with advanced ovarian cancer treated with NAC followed by CRS with HIPEC at 3 and 6 months post-treatment.
- 2.2.2 To describe neurotoxicity in patients with advanced ovarian cancer treated with NAC followed by CRS with HIPEC.
- 2.2.3 To describe abdominal discomfort in patients with advanced ovarian cancer treated with NAC followed by CRS with HIPEC.
- 2.2.4 To describe toxicities in patients with advanced ovarian cancer treated with NAC followed by CRS with HIPEC.
- 2.2.5 To describe the response rate in patients with advanced ovarian cancer treated with NAC followed by CRS with HIPEC.
- 2.2.6 To estimate progression-free survival (PFS) in patients with advanced ovarian cancer treated with NAC followed by CRS with HIPEC.

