5.2 Secondary Outcomes

- 5.2.1 QOL in patients with advanced ovarian cancer treated with SOC NAC followed by CRS with HIPEC as determined by the FACT-O questionnaire at 3 and 6 months post-treatment
- 5.2.2 Neurotoxicity in patients with advanced ovarian cancer treated with SOC NAC followed by CRS with HIPEC as determined by the FACT/GOG-NTX questionnaire
- 5.2.3 Abdominal discomfort in patients with advanced ovarian cancer treated with SOC NAC followed by CRS with HIPEC as determined by the FACT/GOG-AD questionnaire
- 5.2.4 Toxicities in patients with advanced ovarian cancer treated with SOC NAC followed by CRS with HIPEC (for one year post-op) as indicated by the number and severity of adverse events as defined by CTCAE v5.0
- 5.2.5 Response rates using RECIST v1.1 criteria in patients with advanced ovarian cancer treated with SOC NAC followed by CRS with HIPEC – at 3, 6, and 12 months post surgery.
- 5.2.6 PFS in patients with advanced ovarian cancer treated with SOC NAC followed by CRS with HIPEC

A Phase II Trial Evaluating Quality of Life After HIPEC in Patients with Stage IIIC and IV Ovarian, Fallopian Tube or Primary Peritoneal Carcinoma
 Wake Forest Baptist Comprehensive Cancer Center (WFBCCC)
 CCCWFU 83216

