6.2 Treatment Administration

6.2.1 Surgical Intervention and Subsequent Chemotherapy

6.2.1.1 Preoperative Preparation

Patients will have a mechanical and antibiotic bowel preparation. Potential ostomy sites will be marked by the surgeon or the endostomal nurse prior to surgery.

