6.4 Duration of Therapy

Therapy (HIPEC) will be administered for 90 minutes with carboplatin 800 mg/m² during the surgery as described in Section 6.2.1.2 of this protocol.

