13.2 Analysis of Secondary Objective

13.2.1 To describe QOL in patients with advanced ovarian cancer treated with SOC NAC followed by CRS with HIPEC as determined by the FACT-O questionnaire at 3 and 6 months post-treatment, the distribution of QOL at 3 and 6 months post-treatment will be examined. The descriptive statistics of QOL at 3 and 6 months post-treatment will be presented. In addition, the longitudinal data of QOL over time will be displayed graphically with individual trajectories.

13.2.2. To describe neurotoxicity at the end of study, the descriptive statistics will be presented. Since neurotoxicity is a 4-item measure from FACT/GOG-NTX4, counts and percentages will be calculated. Mean and standard deviation will be also calculated.

A Phase II Trial Evaluating Quality of Life After HIPEC in Patients with Stage IIIC and IV Ovarian, Fallopian Tube or Primary Peritoneal Carcinoma
Wake Forest Baptist Comprehensive Cancer Center (WFBCCC)
CCCWFU 83216

13.2.3. To describe abdominal discomfort at the end of study, the descriptive statistics will be presented. The abdominal discomfort is a 4-item score from FACT-GOG/AD. Counts and percentages will be calculated. Mean and standard deviation will be also calculated.

13.2.4. The toxicities will be measured by the number and severity of adverse events defined by CTCAE v5.0. Counts and percentages will be calculated for each adverse event. Mean, standard deviation, median, and interquartile range will be calculated for number of adverse events.

13.2.5. The response rate using RECIST criteria at each time point will be estimated. Counts and percentages will be calculated.

13.2.6. This secondary objective is to estimate progression free survival using survival analysis. Survival will be measured up to the time until progression, date of last contact, or death, whichever comes first. Kaplan-Meier survival curves will be used to estimate the survival probabilities. The survival probabilities for the whole sample and for the stratified groups (weekly or 3-weekly) will be calculated. The log-rank test will be used to compare the two stratified groups.

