Appendix D - SURGERY FORM

[contact]

Patient Initials: _____
Institution: _____

Study ID# 83216
Surgeon _____

DATE of SURGERY ____/____/____

What was the BSA value that the dose was based on?: ____ m² Weight ____ Height ____

- What is the Resection Status after surgery? (circle) R0 R1 R2a R2b R2c
- What was the duration of HIPEC perfusion in minutes? _____ min.
- What is the average Inflow / Outflow temperature (C°)? I _____ / _____
- What was the length of surgical procedure from start to end? _____ hours

Does the Operative Report accompany this form? ____ YES ____ NO

If not, note reason:

Does the Pathology report accompany this form? ____ YES ____ NO

If not, note reason:

Does the Perfusion Record – HIPEC flowsheet accompany this form?

____ YES ____ NO

If not, note reason:

COMMENTS:

Person Completing Form _____

DATE ____/____/____

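### The objective is progression-free survival, but 8.6 defines disease-free survival without death, and 13.2.6 gives neither a time origin nor a censoring rule

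*Combined protocol and SAP*

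**What the plan says.** Section 2.2.6 sets the objective: "To estimate progression-free survival (PFS) in patients with advanced ovarian cancer treated with NAC followed by CRS with HIPEC". Section 5.2.6 lists the matching outcome, "PFS in patients with advanced ovarian cancer treated with SOC NAC followed by CRS with HIPEC", without defining it.

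The section on measuring survival, 8.6, does not mention PFS. It reads: "Disease-free survival will be measured from the time of completion of treatment until the first date that recurrent or progressive disease is objectively documented". It adds that progression is judged against the smallest measurements since treatment began. Disease-free survival appears in neither section 2 nor section 5.

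The analysis text for the PFS objective, 13.2.6, says: "Survival will be measured up to the time until progression, date of last contact, or death, whichever comes first". It continues: "Kaplan-Meier survival curves will be used to estimate the survival probabilities". It also plans a log-rank test between weekly and 3-weekly groups. It does not cite 8.6.

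Two other places bear on the definition. On what treatment means, 6.4 says "Therapy (HIPEC) will be administered for 90 minutes", while 6.2.1 is headed "Surgical Intervention and Subsequent Chemotherapy". On residual tumor, the Surgery Form (Appendix D) asks: "What is the Resection Status after surgery? (circle) R0 R1 R2a R2b R2c".

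**The concern.** A Kaplan-Meier curve needs an origin, an event and a censoring rule. For the trial's only time-to-event objective, the documents do not give these three consistently. Two analysts could each follow the text and produce different curves, and the choice could be made after the data are seen.

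Death matters most. Appendix F offers drug, surgery and complications among the causes of death, so deaths without progression are foreseen. Under 8.6 such a patient never has an event. Under 13.2.6 the clock stops at death, but death stands in the same list as last contact, and nothing says which of the two is an event.

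**Working it through.** **Step 1. The two texts side by side.**

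| Element | 8.6 | 13.2.6 |
|---|---|---|
| Endpoint named | Disease-free survival | PFS |
| Time origin | Completion of treatment, not tied to a date | None given |
| Progression | Event | Ends follow-up |
| Death | Not mentioned | Ends follow-up; not called an event |
| Last contact | Not mentioned | Ends follow-up; not called censoring |
| Population | Label implies patients free of disease | Whole sample |

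Neither column is a full definition, and they differ on death.

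**Step 2. Time origin.** Several places point to the day of surgery. Section 6.4 equates therapy with the 90-minute HIPEC, and 1.3 calls HIPEC a single treatment. The post-treatment visits in 6.1 follow directly on the operating-room day. The primary outcome at 6 weeks post-treatment (5.1.1) is collected at week 6 post-surgery (8.2). Against this stand the heading of 6.2.1 and a mention of subsequent cycles in 7.1.3.1. No post-operative regimen, cycle count or schedule is given under 6.2.1. Surgery is therefore the likelier origin, but 8.6 does not say so.

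**Step 3. Residual tumor.** Section 6.2.1.2 makes removal of all gross tumor a goal, and Appendix D provides for R2a to R2c. Taking R2 in its usual sense of macroscopic residual disease (the form does not define it), these patients are not disease-free at time zero, yet objective 2.2.6 includes them.

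**Step 4. Size of the death rule.** The documents give no PFS rate or event count, so there is no stated figure to reproduce. Inputs:
- n = 50 (13.3).
- S, the 12-month estimate when only progression counts, is assumed to be 0.80 to 0.50 (12-month progression of 20% to 50%).
- One early death without documented progression, while all 50 are at risk.

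With the death as an event, the estimate is S × (1 − 1/50). With the death censored, it is S. The difference is S/50:
- S = 0.80: 0.80/50 = 1.6 points
- S = 0.60: 0.60/50 = 1.2 points
- S = 0.50: 0.50/50 = 1.0 point

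Check with counts: one early death, then 20 progressions among the other 49. Death censored: 29/49 = 59.2%. Death as event: 29/50 = 58.0%. The difference is 1.2 points.

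A later death weighs more because progression has thinned the risk set. If the same death comes after all 20 progressions, with no other censoring, the estimates are 30/50 = 60.0% and 29/50 = 58.0%, a difference of 2.0 points (1/50).

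**Step 5. Several deaths.** Let p be the 12-month risk of progression and d the risk of death without documented progression, with constant hazards. The estimate is (1 − p)(1 − d) with death as an event and 1 − p with death censored, so the difference is (1 − p)d. For assumed p of 20% to 50% and d of 2% to 10%:
- Smallest: 0.50 × 0.02 = 1.0 point
- Example (p = 40%, d = 5%): 60.0% − 57.0% = 3.0 points
- Largest: 0.80 × 0.10 = 8.0 points

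The sign is fixed: replacing an event by a censored time cannot lower a Kaplan-Meier estimate.

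**The case against.** The strongest reply is that the PFS analysis is described in 13.2.6, which names death, and that nothing links it to 8.6. On that view 8.6 describes an endpoint that no analysis uses, and the planned curve does not leave out deaths. Part of this stands. A reader might infer that 8.6 is the only definition, or that the planned analysis ignores death, and the documents support neither. But 13.2.6 stops the clock at death without calling it an event, and 8.6 remains the only section on how survival is measured.

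On the origin, a reader might infer that the clock starts only after later chemotherapy, two months or more after surgery. That needs an assumed post-operative regimen, because the documents specify none, so no size can be given to such a shift.

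On residual tumor, a reader might infer that 8.6 excludes R2 patients. It does not: its event includes progression, judged against the smallest earlier measurement, and that rule can be applied to someone with residual disease. Only the label fails to fit.

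Finally, 13.1 calls the study descriptive, and PFS is secondary with no power target. That stands and limits the importance of the point.

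**Conclusion.** The point holds as an inconsistency to be reconciled. The objective is PFS; 8.6 defines another endpoint that omits death and has no dated start; 13.2.6 covers PFS but lacks an origin and a split between events and censoring.

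If 8.6 were applied, the 12-month estimate could only rise, by about S/50 per early death. The 1.0 to 1.6 point range rests on assumed progression of 50% to 20% and on n = 50. A reader might infer a flat 2 points (1/50) per death. For early deaths, such as post-operative ones, that holds only if nobody progresses; otherwise it is reached only by a death that follows the progressions. The number of such deaths is unknown. The origin and residual-tumor points are gaps in wording, without a supportable size. The primary quality-of-life comparison is not affected.

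**What to change.** Replace the text of 8.6 with one definition and cite it in 13.2.6:

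*PFS is the time from the date of CRS with HIPEC to the first objectively documented progression or death from any cause, whichever is earlier. It applies to all patients treated with HIPEC, whatever their resection status. Patients with neither event are censored at their last disease assessment.*

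The last disease assessment is a better censoring date than last contact, because tumor assessments are at 3, 6 and 12 months. Contact between the last two could otherwise credit up to 6 months (12 − 6) of progression-free time that no scan supports.

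If disease-free survival is also wanted, name it as a separate endpoint and limit it to R0/R1 patients.

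The cost is a wording change and a cross-reference. Surgery date and resection status are on Appendix D, and date of death is on Appendix F. Appendix F has only a yes/no box for progression, so the progression date should come from the scan or the Measurement Form (Appendix G), and the plan should say so. The reported PFS may be slightly less favourable than under 8.6.

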9.0 Adverse Events List and Reporting Requirements

9.1 Adverse Event List

9.1.2 Carboplatin

ADVERSE EXPERIENCES IN PATIENTS WITH OVARIAN CANCER SWOG STUDY				
		Carboplatin Arm Percent*	Cisplatin Arm Percent*	P-Values†

A Phase II Trial Evaluating Quality of Life After HIPEC in Patients with Stage IIIC and IV Ovarian, Fallopian Tube or Primary Peritoneal Carcinoma
 Wake Forest Baptist Comprehensive Cancer Center (WFBCCC)
 CCCWFU 83216

ADVERSE EXPERIENCES IN PATIENTS WITH OVARIAN CANCER SWOG STUDY				
		Carboplatin Arm Percent [*]	Cisplatin Arm Percent [*]	P- Values [†]
Bone Marrow				
Thrombocytopenia	<100,000/mm ³	59	35	< 0.001
	<50,000/mm ³	22	11	0.006
Neutropenia	<2,000 cells/mm ³	95	97	ns
	<1,000 cells/mm ³	84	78	ns
Leukopenia	<4,000 cells/mm ³	97	97	ns
	<2,000 cells/mm ³	76	67	ns
Anemia	<11 g/dL	88	87	ns
	<8 g/dL	8	24	< 0.001
Infections		18	21	ns
Bleeding		6	4	ns
Transfusions		25	33	ns
Gastrointestinal				
Nausea and vomiting		94	96	ns
Vomiting		82	91	0.007
Other GI side effects		40	48	ns
Neurologic				
Peripheral neuropathies		13	28	0.001
Ototoxicity		12	30	< 0.001
Other sensory side effects		4	6	ns
Central neurotoxicity		23	29	ns
Renal				
Serum creatinine elevations		7	38	< 0.001
Blood urea elevations	-	-	-	-
Hepatic				
Bilirubin elevations		5	3	ns
SGOT elevations		23	16	ns
Alkaline phosphatase elevations		29	20	ns
Electrolytes loss				
Sodium	-	-	-	-
Potassium	-	-	-	-
Calcium	-	-	-	-
Magnesium		58	77	< 0.001
Other side effects				
Pain		54	52	ns
Asthenia		43	46	ns

A Phase II Trial Evaluating Quality of Life After HIPEC in Patients with Stage IIIC and IV Ovarian, Fallopian Tube or Primary Peritoneal Carcinoma
 Wake Forest Baptist Comprehensive Cancer Center (WFBCCC)
 CCCWFU 83216

ADVERSE EXPERIENCES IN PATIENTS WITH OVARIAN CANCER SWOG STUDY				
		Carboplatin Arm Percent [*]	Cisplatin Arm Percent [*]	P- Values [†]
Cardiovascular	23	30	ns	
Respiratory	12	11	ns	
Allergic	10	11	ns	
Genitourinary	11	13	ns	
Alopecia [‡]	43	57	0.009	
Mucositis	6	11	ns	

^{*}Values are in percent of evaluable patients
[†]ns = not significant, p > 0.05
[‡]May have been affected by cyclophosphamide dosage delivered

9.2 Adverse Event Characteristics

- Adverse event monitoring will begin at the time of surgery and will continue for six (6) consecutive weeks post-op. AE's will be recorded in WISER at the six-week time point.
- CTCAE term (AE description) and grade:** The descriptions and grading scales found in the revised NCI Common Terminology Criteria for Adverse Events (CTCAE) version 5.0 will be utilized for AE reporting. All appropriate treatment areas should have access to a copy of the CTCAE version 5.0. A copy of the CTCAE version 5.0 can be downloaded from the CTEP web site (<http://ctep.cancer.gov>).
- 'Expectedness':** AEs can be 'Unexpected' or 'Expected' (see Section 7.1 above) for expedited reporting purposes only.
- Attribution** of the AE:
 - Definite – The AE is **clearly related** to the study treatment.
 - Probable – The AE is **likely related** to the study treatment.
 - Possible – The AE **may be related** to the study treatment.
 - Unlikely – The AE is **doubtfully related** to the study treatment.
 - Unrelated – The AE is **clearly NOT related** to the study treatment.

9.3 STRC SAE Reporting Requirements

The Safety and Toxicity Reporting Committee (STRC) is responsible for reviewing SAEs for WFBCCC Institutional studies as outlined in Appendix C. STRC currently requires that all unexpected grade 4 SAEs, all grade 5 SAEs, and any unplanned hospitalizations on these trials be reported to them for review. All WFBCCC Clinical Research Management (CRM) staff members assisting a Principal Investigator in investigating, documenting and reporting an SAE qualifying for STRC reporting are responsible for informing a clinical member of the STRC as well as the entire committee via the email notification procedure of the occurrence of an SAE.

9.4 WFUHS IRB AE Reporting Requirements

Any unanticipated problems involving risks to subjects or others and adverse events shall be promptly reported to the IRB, according to institutional policy. Reporting to the IRB is required regardless of the funding source, study sponsor, or whether the event involves an investigational or marketed drug, biologic or device. Reportable events are not limited to physical injury, but include psychological, economic and social harm. Reportable events may arise as a result of drugs, biological agents, devices, procedures or other interventions, or as a result of questionnaires, surveys, observations or other interactions with research subjects.

All members of the research team are responsible for the appropriate reporting to the IRB and other applicable parties of unanticipated problems involving risk to subjects or others. The Principal Investigator, however, is ultimately responsible for ensuring the prompt reporting of unanticipated problems involving risk to subjects or others to the IRB. The Principal Investigator is also responsible for ensuring that all reported unanticipated risks to subjects and others which they receive are reviewed to determine whether the report represents a change in the risks and/or benefits to study participants, and whether any changes in the informed consent, protocol or other study-related documents are required.

Any unanticipated problems involving risks to subjects or others occurring at a site where the study has been approved by the WFUHS IRB (internal events) must be reported to the WFUHS IRB within 7 calendar days of the investigator or other members of the study team becoming aware of the event.

Any unanticipated problems involving risks to subjects or others occurring at another site conducting the same study that has been approved by the WFUHS IRB (external events) must be reported to the WFUHS IRB within 7 calendar days of the investigator or other members of the study team becoming aware of the event.

Any event, incident, experience, or outcome that alters the risk versus potential benefit of the research and as a result warrants a substantive change in the research protocol or informed consent process/document in order to insure the safety, rights or welfare of research subjects.

